10.3.1 Adverse events

All information obtained on adverse events will be summarized in tabular format.

A subject with multiple adverse events of the same type is only counted once towards the total of that event.

All deaths and serious adverse events will be tabulated.

All AEs, deaths and serious adverse events will be provided in patient listings.

11 Ethical considerations and administrative procedures

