4.2 Rationale for dose/regimen and duration of treatment

Preliminary, publicly available data suggest efficacy of mavrilimumab at a dose of 6 mg/kg IV. However, these results are from an open-label study, and the results from our Phase II randomized, placebo controlled trial may inform the design and dose for larger studies.

In a Phase 1 single-ascending-dose (SAD) study, the pharmacokinetics (PK) of mavrilimumab were tested at doses of 0.01-10 mg/kg in patients with mild-to-moderate RA. Mavrilimumab was well-tolerated in a single IV injection up to 10 mg/kg in subjects with mild to moderate RA at all dose levels. Pharmacokinetic and pharmacodynamic simulations from studies in subjects with RA, coupled with the PK data from the Phase 1 study, indicate that a single dose of ≥ 3 mg/kg will provide EC90 (the concentration that leads to 90% maximal response) for the RA endpoint ACR50 (American College of Rheumatology 50% response criteria; data on file) for up to 22 days. Therefore, at doses ≥ 3 mg/kg, the pharmacologic profiles indicated sustained peripheral inhibition of the GM-CSF-R α signaling axis for at least three weeks.

In preclinical studies, the potential systemic effects of mavrilimumab (CAM-3001) have been investigated in a 4-week and an 11-week repeat dose cynomolgus monkey study. There were no effects attributable to intravenous (IV) administration of CAM-3001 (mavrilimumab) in doses up to 100 mg/kg/week for 4 weeks in a study conducted in accordance with Good Laboratory Practice (GLP). In an 11-week exploratory (non-GLP) study, there were no effects attributable to IV administration of CAM-3001 (mavrilimumab) following 10 mg/kg/week, and the no observed adverse event level (NOAEL) was 100 mg/kg/week. An immunocytochemistry screen to test in vitro binding of CAM-3001 (mavrilimumab) to a panel of normal human tissues revealed no non-specific or unanticipated binding of the antibody. Reference for further details on safety studies in animals and humans is made to the investigator brochure.

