4.3 Risks and benefits

To date, there are no adverse events with a recognized causal relationship to exposure to mavrilimumab. However, there are a number of hypothetical risks that can be extrapolated from the mechanism of action. In particular, GM-CSF antagonism may interfere with immune response to infections. It is unknown how likely these effects are to occur, but their frequency may be lower with a one-time dose as compared to a longer duration to treat a chronic disease.

Frequent side effects:

- Nausea (approximately 1 in 10 subjects, self-limiting)
- Nasopharyngitis (approximately 1 in 10 subjects, self-limiting)
- Headache (approximately 1 in 10 subjects, self-limiting)

Rare but potentially life-threatening adverse reaction:

- Severe hypersensitivity reactions: While these have not been reported with Mavrilimumab, such reactions (including anaphylaxis, anaphylactoid reactions, cytokine release, and endotoxemia) have been observed after administration of other monoclonal antibodies. These reactions may be severe and may result in death.
- Leukopenia resulting in an increased risk of opportunistic infections. Mavrilimumab reduces the number of neutrophils. In some patients the reduction may be such to expose to additional (opportunistic) infection.

Additional potential side effects (of unknown frequency):

- Pulmonary alveolar proteinosis (PAP): studies have linked blockage of GM-CSF, the target of Mavrilimumab, with PAP. While the use of Mavrilimumab has not been

associated with the development of PAP in patients, a potential risk for this complication with Mavrilimumab use may exist.

- While the use of Mavrilimumab has not been associated with the development of cancer, drugs that modulate the immune response may increase the risk of cancer.
- Impaired response to vaccines. Drugs that reduce the immune response, like Mavrilimumab can impair the immune response to vaccine.
- Antibodies that inactivate the study drug thus losing its efficacy

In general, the risk to subjects in this trial may be minimized by compliance with the eligibility criteria and study procedures, close clinical monitoring, as well as periodic review of all safety data by an independent data monitoring committee (DMC).

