Assessment for “respiratory failure” as defined for the secondary endpoint														X
Assessment of survival (day of death if occurs) ^m	X											X	X	
Mavrilimumab/placebo administration		X												

^a Given resource limitation related to COVID-19, all laboratory testing is considered standard of care, though as possible, certain tests that are not considered standard of care may be obtained for research. If the laboratory tests in the schedule of activities are obtained, they will be documented accordingly. If laboratory tests cannot be obtained for other reasons, such as requiring extra use of personal protective equipment, unnecessary exposure to healthcare personnel, or safety issues related to obtaining and processing samples, these will not be considered a protocol deviation.

^b Study visits are planned for hospitalized patients only; planned activities that fall on study days that occur after the patient is discharged will not be done.

^c Screening activities can occur from -3 and 0 days before enrollment except for 2019-nCoV testing, which can occur between -7 and 0 days before enrollment.

^d For hospitalized patients, this visit will include the activities listed. For patients who have been discharged before Study Day 28, this visit will be conducted by phone/telehealth but will not include any laboratory tests.

^d An unscheduled visit is planned to occur on the day of discharge if the patient is discharged before Day 28; in which case this will serve as an early termination visit. If patient is discharged the visit on Study Day 28±3 and Study Day 60±3, will be done by telephone call follow-up and lab tests will not be performed. May also be used for adverse event assessments.

* Nasopharyngeal or oropharyngeal swabs for SARS-CoV2 RNA levels will be performed until negative or discharge. Sampling will include both nostrils, or repeat sampling will include the same nostril if only one nostril is used. A local sample will be used for inclusion criteria, and as possible appreciating the concerns related to extra use of personal protective equipment and exposure to healthcare personnel

"For the purposes of the primary end-point and time to freedom from supplemental oxygen, the ordinal scale and presence of supplemental oxygen will be assessed daily thru Day 14 while hospitalized. If patient has been discharged prior to Day 14, it will be assessed on Day 14, 21 and 28.

^e Collect at least baseline and at least weekly thereafter.

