10.1 Analysis sets

All patients who provide informed consent and are randomized will be included in the analysis. Specifically, patients who are randomized and do not receive study medication/placebo and patients who have the study infusion discontinued before completion will remain in the intention-to-treat analysis. However, we may also perform a secondary, exploratory modified intention to treat analysis that would include all patients that actually receive study drug or placebo. As noted above, for patients who are lost to follow-up, due diligence will be performed, and given the importance of reliable estimates of the treatment effect for planning futures, every effort will be made to document respiratory status and survival as outlined in the primary and secondary endpoints.

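### Study blood tests stop at discharge and the adverse event table carries no observation time, so crude counts may understate silent laboratory events on mavrilimumab if it shortens hospital stay

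*Combined protocol and SAP*

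**What the plan says.** On counting, Section 10.3.1 of the combined protocol and SAP says: "A subject with multiple adverse events of the same type is only counted once towards the total of that event". It promises tables and patient listings, but states no denominator, follow-up time or rate. Section 10.1 says "All patients who provide informed consent and are randomized will be included in the analysis" and defines no separate safety set. It allows an optional exploratory analysis of patients who received drug or placebo.

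On blood tests, the footnotes to Table 7-1 (Section 7.1) say that "planned activities that fall on study days that occur after the patient is discharged will not be done". The last opportunity for a draw is the discharge visit: "An unscheduled visit is planned to occur on the day of discharge if the patient is discharged before Day 28". For patients already at home, the Day 28 visit is remote: "this visit will be conducted by phone/telehealth but will not include any laboratory tests". The Day 28 and Day 60 contacts "will be done by telephone call follow-up and lab tests will not be performed". In hospital, laboratory tests are treated as standard of care, and those that cannot be obtained for reasons such as saving protective equipment or limiting staff exposure are not deviations.

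On what the tests are for, the safety schedule in Section 9.1.6 uses the blood count to look for leukopenia, neutropenia and thrombocytopenia, and the liver profile to look for drug-induced liver injury. Section 4.3 says "Mavrilimumab reduces the number of neutrophils". Section 4.2 expects "sustained peripheral inhibition of the GM-CSF-R α signaling axis for at least three weeks" at doses of 3 mg/kg or more. Section 9.1.1 continues adverse event monitoring for at least 60 days after dosing.

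**The concern.** A silent fall in neutrophils or rise in liver enzymes is found only if blood is drawn. Under this plan the study draws no blood after discharge, although the expected pharmacological effect may outlast the stay. A patient who goes home early therefore has less chance of such an event being recorded, yet counts as one subject in the table, the same as a patient observed for weeks.

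The trial hopes that mavrilimumab speeds recovery, and length of hospitalization is a secondary objective. If that hope is met, laboratory observation will be shorter on mavrilimumab and the comparison of crude counts will tilt in its favour. Safety is also a secondary objective, and the results are meant to inform Phase III. The risk is a table that reassures only because one arm was tested for less time.

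The once-per-subject rule is an ordinary convention and is not the defect. What is missing is any statement of who was tested and for how long.

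**Working it through.** The plan has no figure on this point to reproduce. It gives no expected length of stay and no onset timing, so the calculations below show direction and sensitivity only. Every stay and every risk in them is an assumption.

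**Model.** Onset hazard h is constant to Day 28. Stay is exponential with rate λ = 1/mean stay. An event is seen only if it starts before both discharge and Day 28.

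- Hazard from the 28-day risk r: h = −ln(1 − r)/28.
- Proportion of subjects with a detected event: h/(h + λ) × (1 − exp(−28(h + λ))).

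**One case in full.** Assume true 28-day risks of 20% on mavrilimumab and 10% on placebo (true ratio 2), and mean stays of 7 and 14 days.

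- Placebo: h = 0.00376, λ = 0.0714. Detected = 0.0500 × 0.878 = 0.044.
- Mavrilimumab: h = 0.00797, λ = 0.1429. Detected = 0.0528 × 0.985 = 0.052.
- Apparent ratio: 0.052/0.044 = 1.18.
- Expected detected cases in 30 patients: 1.6 and 1.3.

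**Range, for an assumed placebo risk of 5% to 20%.**

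| Mean stay, mavrilimumab vs placebo (days) | Apparent ratio if true ratio is 1 | Apparent ratio if true ratio is 2 |
|---|---|---|
| 10 vs 10 | 1.00 | 2.02–2.12 |
| 8 vs 10 | 0.83 | 1.68–1.78 |
| 10 vs 14 | 0.78 | 1.57–1.66 |
| 7 vs 14 | 0.57–0.58 | 1.16–1.25 |

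**Dependence on onset timing.** Suppose everyone on mavrilimumab leaves on Day 7 and everyone on placebo on Day 14.

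- Onset uniform over 7 days: both arms capture all events, and the ratio of fractions seen is 1.00.
- Onset uniform over 14 days: fractions 7/14 and 14/14, ratio 0.50.
- Onset uniform over 28 days: fractions 7/28 and 14/28, ratio 0.50.

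A shorter stay alone therefore does not produce the bias. Some onsets must also fall after the last draw.

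**Effect of using observation time.** In this model, expected events divided by expected observed days equals h in each arm. The rate ratio is 1.00 when the risks are equal. When they are 20% and 10% it is 0.00797/0.00376 = 2.12, which is the true hazard ratio. This result depends on discharge being unrelated to the risk of the event, which will not hold exactly in practice.

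**What the model leaves out.** It has no deaths, although death also ends laboratory observation. It assumes that any event in hospital is detected at once, whereas actual draws are intermittent and may be missed.

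**The case against.** The strongest reply is that little is lost and little turns on it. Section 9.1.1 makes a laboratory abnormality an adverse event only if it causes signs or symptoms, is clinically significant or needs therapy. Symptomatic consequences, and findings from outside care, remain reportable for 60 days. Secondary infections, the harm that Section 4.3 links to leukopenia, are on the safety schedule through Day 60. Only silent, clinically significant abnormalities that begin after the discharge draw are missed. The table is descriptive, full listings are provided, a data monitoring committee with access to assignments reviews safety, and one or two cases per arm would settle nothing. All of this stands. It makes the point a modest one, but it does not supply the missing numbers tested or observation time.

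It is also fair to say that Section 10.3.1 states no denominator. A reader might infer from Section 10.1 that events are divided by all randomised patients, but the text does not say so. The point does not depend on it: a count over dosed patients ignores observation time just as much.

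A reader might also infer that signals are certainly understated, or put a size on it by treating the design rates of 80% and 40% (Section 10.3) as discharge rates by Day 14. With λ = −ln(1 − p)/14 and a 22-day window, that gives 8.0 and 15.1 mean observable days. At an equal daily hazard of 0.005, detected incidence is then 3.9% and 7.2%, as if the drug were 46% safer. The documents do not support using these figures as estimates. Section 10.3 counts success whether or not the patient is still in hospital, and counts deaths and missing data as failures; Section 2 foresees discharge on oxygen. For the same reasons, the rates cannot be turned into numbers still in hospital for a Day 14 blood count. Nor does three weeks of receptor inhibition show that neutropenia starts late, and Section 4.3 names no hepatic risk.

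**Conclusion.** The point holds conditionally. Study laboratory tests end at discharge, and the adverse event table takes no account of how long each arm was tested. The crude counts may understate silent laboratory events on mavrilimumab relative to placebo if two things are true: stay is shorter on mavrilimumab, and some events start after the discharge draw. Both are plausible on the plan's own hypothesis and stated duration of effect, but neither is established.

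The size cannot be computed from the documents. Over the assumed stays shown, a true ratio of 2 appears as anything from about 1.2 (7 vs 14 days) to 2.1 (equal stays). If all onsets precede discharge, nothing is lost. More deaths on placebo would shorten its observation too and partly offset the imbalance.

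This is a reporting improvement worth making because it is cheap. It does not show that the safety comparison is invalid, and no reanalysis can recover tests that were never drawn.

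**What to change.** In Section 10.3.1, state the denominator and keep the crude subject counts. For leukopenia, neutropenia, thrombocytopenia and liver test abnormalities, add by arm:

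- (a) the number of patients with at least one post-dose value, and the median days from infusion to the last laboratory value;
- (b) the proportion abnormal at each visit among patients tested, with an early comparison as the view least affected by discharge (Day 3 for the blood count, the post-dose day that both schedules appear to share), and a statement that it says nothing about later onset;
- (c) events per patient-day of laboratory observation, as a supportive display, with a statement that it is affected by selection because patients still in hospital are sicker.

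Before the by-visit table is fixed, reconcile Table 7-1 with the safety schedule in Section 9.1.6. The haematology and liver profile days appear to differ, although column positions may have shifted when the tables were read. A Table 7-1 footnote also appears to limit the differential count to screening, while the safety schedule lists it with every blood count. By-visit neutrophil results depend on which applies.

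The cost is SAP wording and one or two descriptive tables from data already collected, with no new tests or visits. Estimates will be imprecise with 30 patients per arm, and the text should say so.

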11.1 Regulatory and ethical compliance

This clinical study was designed and shall be implemented, executed and reported in accordance with the ICH Harmonized Tripartite Guidelines for Good Clinical Practice, with applicable local regulations US CFR 21, and with the ethical principles laid down in the Declaration of Helsinki.

11.2 Responsibilities of the investigator and IRB

Before initiating a trial, the investigator/institution must obtain approval/favorable opinion from the Institutional Review Board (IRB) for the trial protocol, written informed consent form, consent form updates, subject recruitment procedures and any other written information to be provided to subjects.

The protocol will be registered in a publicly accessible database such as clinicaltrials.gov. In addition, after study completion and finalization of the study report the results of this trial will be submitted for publication and posted in a publicly accessible database of clinical trial results.

This protocol defines the study objectives, the study procedures and the data to be collected on study participants. Additional assessments required to ensure safety of subjects should be administered as deemed necessary on a case by case basis. Investigators will apply due diligence

to avoid protocol deviations. If an investigator feels a protocol deviation would improve the conduct of the study this must be considered a protocol amendment, and unless such an amendment is agreed upon by sponsor/investigator and approved by the FDA and IRB, where required, it cannot be implemented.

12 Protocol adherence

This protocol defines the study objectives, the study procedures and the data to be collected on study participants. Additional assessments required to ensure safety of subjects should be administered as deemed necessary on a case by case basis. Investigators ascertain they will apply due diligence to avoid protocol deviations. If an investigator feels a protocol deviation would improve the conduct of the study this must be considered a protocol amendment, and unless such an amendment is agreed upon by Kiniksa and approved by the IRB/IEC and health authorities, where required, it cannot be implemented.

